7.6.2 Description of Activities

The following data will be documented (if assessed in routine care):

Physician:

Baseline Visit (Week 0)

1) Informed consent

2) Patient Background

- Patient ID code
- Demographic Data; Birth date or age, Sex (pregnant/lactation), Race, Weight
- Patient status (out-patient, in-patient)
- Duration of illness
- Indication for the current adalimumab therapy
- Complications
- Past illness
- History; Smoking history, History of allergy
- Progression of RA; Severity of RA (Stage), Functional class of RA (Class)

3) Previous treatment of RA; Biologics, DMARDs, Corticosteroids

4) Inclusion / Exclusion criteria

- Inclusion criteria; Age ≥ 16 years old, Duration of RA ≤ 2 years, MTX dose ≥ 12 mg/week, MTX administration ≥ 3 months, DAS28-CRP > 3.2
- Exclusion criteria; Patients who have been previously treated with biologics

5) Current treatment with adalimumab

6) Current concomitant drug treatment

- MTX (From 6 months before adalimumab treatment to current)
 - DMARDs except MTX
-

- Corticosteroids
 - Other concomitant drugs
- 7) Current non-drug treatment for RA
- 8) Current status
- Disease activity (Visual Analog Scale by the physician / VAS evaluation)
 - Joint status (28 joints; tender, swollen)
 - Laboratory values (CRP, ESR)
 - X-rays of Hands and Feet

Follow-up Visits (Week 12, 24, 52, 76, 104, last visit)

- 1) Current treatment with adalimumab
- 2) Current concomitant drug treatment
- MTX
 - DMARDs except MTX
 - Corticosteroids
 - Other concomitant drugs
- 3) Current non-drug treatment for RA
- 4) Current status
- Disease activity (Visual Analog Scale by the physician / VAS evaluation)
 - Joint status (28 joints; tender, swollen)
-

- Laboratory values (CRP, ESR)
- X-rays of Hands and Feet (Week 52, 104)
- (S) AE
- Discontinuation of adalimumab treatment (Reason for discontinuation)

Patient:

Baseline Visit (week 0)

- 1) Informed consent
- 2) Disease activity (Visual Analog Scale by the patient / VAS evaluation)
- 3) HAQ
- 4) EQ-5D

Follow-up Visits (Week 12, 24, 52, 76, 104, last visit)

- 1) Disease activity (Visual Analog Scale by the patient / VAS evaluation)
- 2) HAQ
- 3) EQ-5D

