10.1. Overall

Name of data	Derivation and calculation methods
Age	The age on the start date of treatment should be calculated. However, if the birth date is unknown, the age described in the CRF should be used. Since it is obtained up to birth month and year in the CRF, the birth date should be the 1st of the month.
Number of survey institutions	It should be tabulated by institution code.
Number of patients surveyed	It should be tabulated by case (number).
Calculation of period	Period = the relevant date - the initial date +1
Definition of unit period	One week should be converted into seven days.
Date of initial Humira treatment	Of the start dates of treatment in Humira treatment status, the earliest date should be the date of initial Humira treatment.
Date of final Humira treatment	
Of the completion dates of treatment in Humira treatment status, the latest date should be the date of final Humira treatment.
 
However, the following measures should be taken according to the final record of each patient.
 
 • For patients whose the start date of treatment exceeds the planned completion date of each CRF and the completion date of treatment is described as “continuing,” the start date of treatment should be complemented to the complete date of treatment of the record. • For patients whose the start date of treatment is prior to the planned completion date of each CRF and the completion date of treatment is described as “continuing,” the completion date of treatment should be complemented to the complete date of treatment of each CRF. • If the start date of treatment with a biological product and the final record of the completion date of Humira treatment are the same date in the third CRF, the completion date of Humira treatment should be -1 day and the overlap of the treatment period should be deleted. 
*Planned completion date of each CRF First CRF: start date of Humira treatment + 167 days Second CRF: start date of Humira treatment + 363 days Third CRF: start date of Humira treatment + 727 days

Period to treatment completion (day)	It should be between the date of initial Humira treatment and the date of final Humira treatment.

Name of data	Derivation and calculation methods

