Presence of complication: others	Patients with the complication items applicable to the details of blood disorders [diabetes mellitus, gastrointestinal disorder, osteoporosis, malignant tumour, demyelinating disorders, collagen disorders (other than rheumatoid arthritis), others] should be handles as “present,” when there is no description in the presence of complications, it should be handled as “undescribed,” respectively, and others should be handled as “absent.”
Presence of a past history	When any of the details of the past history is evaluated as present, it should be handled as “present,” when it is described as no complication, it should be handled as “absent,” and when there is no description both in past history and the details, it should be handled as “undescribed.”

Name of data	Derivation and calculation methods
Presence of a history of allergy	If there is nothing applicable to a history of allergy, it should be handled as “undescribed.” In the details, if the patient is applicable to both “drugs” and “food,” it should be handled as “both.”
RA stage/progression	If there is no description in the RA stage/progression, it should be handles as “undescribed.”
Disabilities in RA	If there is no description in the RA disability index, it should be handles as “undescribed.”
Presence of concomitant drugs (At start date of Humira treatment)	If there is any drug administration on the date of initial Humira treatment, it should be handled as “present,” and others should be handled as “absent.”
Presence of concomitant drugs (During treatment with Humira)	If there is any drug administration during treatment with Humira, it should be handled as “present,” and others should be handled as “absent.” Administration during treatment with Humira refers to all administration cases not applicable to the followings. 
 • The completion date of treatment with a concomitant drug is prior to the date of initial Humira treatment • The start date of treatment with a concomitant drug is after the date of final Humira treatment
Concomitant drug: MTX (mg/week)	The dose of MTX during the period including the date of initial Humira treatment should be sorted into the following three categories: “ ≥ 12.0 mg/week and < 14.0 mg/week,” “ ≥ 14.0 mg/week and < 16.0 mg/week,” and “ ≥ 16.0 mg/week.”

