Start date of MTX treatment *Per record	When there is more than one record of the same reason for use and same dose within the same patient and the treatment period is overlapped in these records, the information in the record in the latest CRF should be adopted and the start date of MTX treatment of the record should be used. The records with the dose of 0 mg should be excluded from the analysis.
Completion date of MTX treatment *Per record	When the completion date of treatment in the information on the previous treatment and the start date of treatment in the information on the relevant treatment are the same date within the same patient, the completion date of treatment in the information on the previous treatment should be - 1 day.
Treatment continuing group	Among the patients included in the efficacy analysis set (third CRF), patients who are continuously receiving Humira at week 104.

Name of data	Derivation and calculation methods
Treatment discontinued group	Among patients included in the efficacy analysis set (third CRF), patients whom the discontinuation date of Humira treatment and the relevant date at week 104 is ≥ 24 weeks apart of the patients continuing the survey who discontinued Humira treatment later than week 52. Or the patients whom the date of final follow-up (or the lower date of the start date of treatment with other biological product other than Humira) is ≥ 24 weeks apart from the date of Humira treatment discontinuation among the patients discontinued survey who discontinued Humira treatment later than week 52.
Survey discontinued group	Among the patients included in the efficacy analysis set (third CRF), the patients with the entry of the start date of treatment with other biological products other than Humira or the final follow-up date not applicable to the conditions for the treatment discontinued group.
Other groups	Among the patients included in the efficacy analysis set (third CRF), patients who are not applicable to the treatment continuing group, treatment discontinued group or survey discontinued group.

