Purpose of analysis: To indicate the number of patients by evaluation time and the summary statistics of the score and the response for the joint space narrowing score and conduct a paired t test for the response from baseline. Additionally, the number and percentage of the patients by evaluation time by the category of the joint space narrowing score should be shown. The category of the joint space narrowing score should follow “11. Data-layer separation.”

Note: None in particular.

“Table 6.11.2 Percentage of patients without a trend or worsening of the joint space narrowing score (evaluation time at week 104)”

Analysis object: Patients included in the efficacy analysis set (mTSS at week 104)

Purpose of analysis: To tabulate the patients included in the efficacy analysis set (mTSS at week 104) by using the same tabulation technique as Table 6.11.1.

Note: None in particular.

“Table 7.1 Summary of MTX at each Period”

Analysis object: patients included in the safety analysis set

Purpose of analysis: to calculate the summary statistics of the MTX dose at treatment start, the mean MTX dose between treatment start and week 52, the mean MTX dose between treatment start and week 12, and the mean MTX dose between week 12 and week 52.

Note: This form should be prepared only at the time of literature analysis.

“Table 7.1.1 Summary of MTX Over Time”

Analysis object: Patients included in the safety analysis set

Purpose of analysis: To illustrate the followings by timing by a cumulative bar chart: MTX dose at treatment start, MTX dose at week 12, MTX dose at week 24, MTX dose at week 52, MTX dose at week 76, and MTX dose at week 104. At treatment start, at weeks 12, 24, 52, 76 and 104 should be established by the categories indicated in “12. Handling of data on test/evaluation time.”

Note: This form should be prepared only at the time of literature analysis.

“Table 7.1.2 Demographic data and baseline score each MTX Dose of Baseline”

Analysis object: Patients included in the efficacy analysis set

Purpose of analysis: To calculate the number and percentage of patients by patient background factor at the start of treatment, or the stratified summary statistics of MTX dose at the start of Humira treatment.

The patient background factors should follow “11. Data-layer separation.”

Note:

[Complication: liver disorders (hepatitis)]: The denominator of the percentage should be the number of patients with “hepatitis.”

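### The SAP 10.1 rule for overlapping same-dose MTX records can drop earlier exposure, including the dose at Humira start, if a later CRF re-enters the dose with a new, overlapping start date

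*SAP*

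**What the plan says.** SAP 10.1 (Overall) has two consecutive rows on MTX records.

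- **Start date of MTX treatment.** The rule is triggered by "more than one record of the same reason for use and same dose within the same patient and the treatment period is overlapped". Its instruction is that "the information in the record in the latest CRF should be adopted and the start date of MTX treatment of the record should be used".
- **Completion date of MTX treatment.** If one record ends on the date the next begins, "the completion date of treatment in the information on the previous treatment should be - 1 day". The earlier record is shortened and kept. The SAP does not say which of the two rules is applied first.

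The baseline dose is read from these records: "The dose of MTX during the period including the date of initial Humira treatment should be sorted into the following three categories" (12 to under 14, 14 to under 16, and 16 mg/week or more). Neither this row nor SAP section 11 provides an undescribed level for MTX dose, and SAP 9.1 rules out filling in missing data. Table 7.1 also needs "the mean MTX dose between treatment start and week 12".

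On data collection, Protocol 7.6.2 asks at the baseline visit for "MTX (From 6 months before adalimumab treatment to current". The follow-up visits list MTX without a look-back. For Humira itself, SAP 10.1 protects the first date: "Of the start dates of treatment in Humira treatment status, the earliest date should be the date of initial Humira treatment". There is no matching line for MTX.

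**The concern.** The evident aim is one record per unchanged dose. The rule gets there by replacing the earlier record, not by joining the two. That is harmless if the later record carries the original start date. If the later record starts at its own CRF period and still overlaps the earlier one, everything before the new start disappears. If the new start falls after the first Humira injection, no record covers that date.

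MTX dose is the exposure that defines this study, so two kinds of result depend on these records:

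- **Baseline-MTX strata.** Tables 2.1 and 5.4 take their factors from SAP section 11, and Table 6.8.1 takes its factors from Table 5.4. None of the three is marked as literature-only.
- **MTX-dose tables.** These are 5.2.3, 5.2.4, 6.2.2, 6.2.4 to 6.2.7.x and 7.1.x, most of them marked for the literature analysis only.

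Table 6.2.5 is the most sensitive of these, because it divides patients at a mean of 12.0 mg/week up to week 52.

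**Working it through.** The plan states no figure for this rule, so there is none to reproduce. The check applies the rule as written to assumed records.

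**Inputs from the documents.** Day 0 is the date of initial Humira treatment. Planned CRF ends are "First CRF: start date of Humira treatment + 167 days", then +363 and +727 days (SAP 10.1). Weeks 0-52 are days 0 to 363, which is 364 days.

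**Assumptions.** The record dates below are invented. Overlaps are resolved in CRF order. Mean dose is day-weighted over recorded days, because the SAP does not define the denominator.

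**Stable 12 mg/week from day -100**

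| Records entered | Result under the rule | Baseline dose | Days 0-363 covered |
|---|---|---|---|
| A. All CRFs repeat day -100 as start | one record from day -100 | 12 | 364 |
| B. Records share one date at days 168 and 364, overlap rule applied first | one record from day 364 | none | 0 |
| C. Records abut (to 167; 168-363; 364-727) | all three kept | 12 | 364 |
| D. CRF 1 to day 174, CRF 2 from day 168, CRF 3 from day 364 | CRF 1 record dropped | none | 363 - 168 + 1 = 196 |

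In D, 364 - 196 = 168 days are lost (168/364 = 46%), including all of weeks 0-12. If the one-day trimming is applied first, B becomes C and nothing is lost. Keeping the earliest start gives 12 mg/week at baseline and 364 days covered in all four cases.

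**Patients who also change dose.** In each case the second CRF re-enters the dose in use at day 168 with that day as its start, while the first CRF's record runs past it (for example to day 174).

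1. 16 mg to day 200, then 8 mg.
   - Joined: (201 × 16 + 163 × 8)/364 = 4520/364 = 12.42.
   - Rule: (33 × 16 + 163 × 8)/196 = 1832/196 = 9.35.
   - The patient moves from the ≥ 12.0 to the < 12.0 group of Table 6.2.5.
2. 12 mg to day 250, then 8 mg.
   - Joined: (251 × 12 + 113 × 8)/364 = 3916/364 = 10.76.
   - Rule: (83 × 12 + 113 × 8)/196 = 1900/196 = 9.69.
   - Both are below 12.0.
3. 16 mg to day 80, then 12 mg.
   - Joined: (81 × 16 + 283 × 12)/364 = 4692/364 = 12.89.
   - Rule: (81 × 16 + 196 × 12)/277 = 3648/277 = 13.17.
   - Both are above 12.0.

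The error can go in either direction, and it changes a Table 6.2.5 group only in some patients. In cases 1 and 2 the baseline dose is lost as well. In case 3 it survives, because the 16 mg record is untouched.

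**The case against.** The strongest reply is that the harm needs a data pattern the documents do not show. A later CRF must give a new start date, for the same dose and reason, that still overlaps the earlier record. The natural source of same-dose overlap is one course re-entered with its original start and an updated end. For that pattern the rule is sound de-duplication, because the latest CRF has the most current end date. A second-CRF record that starts at day 168 simply abuts a first-CRF record closed at day 167. SAP 10.1 closes continuing Humira records at the planned CRF end. It says nothing equivalent for MTX, so reading a continuing MTX record as open-ended is an assumption. Same-day hand-offs are rescued if the trimming rule is applied first. All of this stands, and it makes the problem conditional. It does not remove it, because the SAP neither requires the original start date to be repeated nor states the order of the two rules.

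A reader might also infer that the loss falls selectively on patients with an unchanged dose and so biases their mean dose. The documents do not support that. In a truly stable patient the mean over recorded days is still 12, or is missing. The wrong means in the working all belong to patients whose dose changed.

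Lost baselines would also not be wholly hidden. Every eligible patient must be on MTX at Humira start, so the MTX strata in Tables 2.1 and 5.4 would fail to add up to the number analysed. That helps detection, but no such check is planned.

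**Conclusion.** The point holds conditionally. As written, the rule gives a wrong result in a plausible case that the SAP does not exclude. In that case the baseline MTX class can be unassignable, and a week 0-52 mean can shift. The three illustrative patients shift by +0.3, -1.1 and -3.1 mg/week, and only the last crosses the 12.0 cut. These sizes rest on invented record dates and a day-weighted mean over recorded days.

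The share of patients affected cannot be derived from the documents. It ranges from none, if later CRFs repeat the original start or records only abut, to every patient whose unchanged dose was re-entered with a new, overlapping start.

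It would be a mistake to read this as a threat to the primary result. The proportion with DAS28-CRP below 2.6 at week 52 uses no MTX record, and the MTX dose for eligibility is a separate item at the baseline visit (Protocol 7.6.2). What is exposed is the baseline-MTX strata and the mostly literature-only MTX-dose tables. That justifies correcting the rule but has no bearing on the main conclusion.

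**What to change.** Amend the two MTX rows of SAP 10.1 as follows:

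1. For overlapping records with the same reason and same dose, keep one record with the earliest start date and the latest CRF's completion date. If the later CRF documents a correction of the start date, use the corrected date. Taking the completion date from the latest CRF lets an updated end date stand.
2. Apply the one-day trimming for coinciding dates before the overlap rule.
3. Check that every eligible patient has an MTX record covering the date of initial Humira treatment, and list any who do not. Running the same check under the present rule shows how many patients were affected at baseline.

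The cost is a small programming change, with no new data. Where later CRFs repeat the original start date, the output is unchanged.

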9.1. Handling of missing data

Missing data should not be complemented in the analysis.

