“Table 6.2.3 Change of DAS28-4CRP Over Time”

Note: The patients included in the efficacy analysis set (DAS28-4CRP) should be handled as the analysis objects and tabulated by DAS28-4CRP category.

“Table 6.3.1 Change of CDAI Over Time”

Note: The patients included in the efficacy analysis set (CDAI) should be handled as the analysis objects and tabulated by CDAI category.

“Table 6.4.1 Change of SDAI Over Time”

Note: The patients included in the efficacy analysis set (SDAI) should be handled as the analysis objects and tabulated by SDAI category.

“Table 6.5.1 Change of HAQ-DI Over Time”

Note: The patients included in the efficacy analysis set (HAQ-DI) should be handled as the analysis objects and tabulated by HAQ-DI category.

The above figures and tables should be prepared only at the time of literature analysis.

“Table 6.2 DAS28-4CRP response, trend, percentage of remission”

Analysis object: Patients included in the efficacy analysis set (DAS28-4CRP)

Purpose of analysis: To indicate the number of patients and summary statistics of the score and response by evaluation time for the DAS28-4CRP and conduct a paired t test for the response from baseline. In addition, the number and the percentage of patients, number of patients with Low+Remission and Remission, point estimate and 95% CI of the percentage by DAS28-4ESR category by evaluation time should be indicated, and McNemer test should be performed for the percentage change from baseline.

The DAS28-4CRP category should follow “11. Data-layer separation.”

Note: The same form should also be prepared in literature analysis.

“Table 6.2.2 Summary of DAS28-4CRP by each Visit per Increase/decrease MTX Dose of up to Week 52 (literature analysis)”

Analysis object: Patients included in the efficacy analysis set (DAS28-4CRP)

Purpose of analysis: To indicate the number of patients by evaluation time, and the summary statistics of the scores and response for the DAS28-4CRP scores stratified by the groups based on the increase and decrease of MTX dose at week 52 and conduct a paired t test for the response from baseline.

The response should be compared between the groups by analysis of variance by evaluation time.

Note: It should be categorized by the following three categories based on the increase and decrease of the MTX dose from the start of Humira treatment to week 52: “ $2 \leq$,” “ $-2 < < 2$,” and “ < -2 .”

This form should be prepared only at the time of literature analysis.

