“Table 6.2.4 Summary of DAS28-4CRP by each Visit per Baseline MTX Dose”

Analysis object: Patients included in the efficacy analysis set (DAS28-4CRP)

Purpose of analysis: To indicate the number of patients by evaluation time, and summary statistics of the score and response for the DAS28-4CRP score by the group of MTX dose at the start of Humira treatment.

In addition, paired t tests should be performed for the response from the start of treatment, and the results of intergroup comparison by analysis of variance should be calculated by evaluation time.

Note: The group separation should follow the concomitant MTX dose (mg/week) in the patient background in “11. Data-layer separation.”

This form should be prepared only at the time of literature analysis.

“Table 6.2.5 Summary of DAS28-4CRP by each Visit per Average Usage MTX Dose of up to week 52”

Analysis object: Patients included in the efficacy analysis set (DAS28-4CRP)

Purpose of analysis: To indicate the number of patients by evaluation time, and summary statistics of the score and response for the DAS28-4CRP score by two groups of the mean MTX dose at week 52: < 12.0 mg/week group or ≥ 12.0 mg/week group. In addition, paired t tests should be performed for the response from baseline, and the results of intergroup comparison by analysis of variance should be calculated by evaluation time.

Note: It should be categorized by the following two categories based on the increase and decrease of the mean MTX dose from the start of Humira treatment to week 52: “< 12.0” and “12.0 \leq .”

This form should be prepared only at the time of literature analysis.

“Table 6.2.6 Univariate logistic analysis event: DAS28-4CRP ≤ 2.6 at week 104”

Analysis object: Patients included in the efficacy analysis set (DAS28-4CRP)

Purpose of analysis: To conduct univariate logistic regression analysis with the number of patients meeting the week 104 DAS28-4CRP < 2.6 as the objective variable and each patient background factor as the explanatory variable, and to indicate the number of patients analyzed, number of patients who developed ADRs, incidence rate, odds ratio, CI and p values.

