To handle the followings as the categorical data: [consultation category (outpatient, inpatient)], [gender (male, female)], [age category (< 15, ≥ 15 and < 30, ≥ 30 and < 50, ≥ 50 and < 65, and ≥ 65 and < 75, ≥ 75 and < 85, ≥ 85)], [age category: (< 15, ≥ 15 and < 65, ≥ 65)], [weight category (< 30, ≥ 30 and < 40, ≥ 40 and < 50, ≥ 50 and < 60, ≥ 60)], [category for duration of illness (< 3 months, ≥ 3 months and < 6 months, ≥ 6 months)], [complication (present, absent)], [smoking history (absent, present)], [RA stage/progression (Stage I/Stage II, Stage III/Stage IV)], [RA disability level (Class I/Class II, Class III/Class IV)], [past history (absent, present)], [history of allergy (absent, present)], [MTX at treatment start (≥ 12.0 mg/week and < 14.0mg/week, ≥ 14.0 mg/week and < 16.0mg/week, ≥ 16.0 mg/week)], [DMARDs at treatment start (excluding MTX) (absent, present)], [adrenocortical hormones at treatment start (absent, present)], [DMARDs during treatment (absent, present)], [adrenocortical hormones during treatment (absent, present)], [other concomitant drugs during treatment (absent, present)], [DAS28-4CRP at treatment start (< 2.6, 2.6 \leq)]; and also indicate the results for [age], [weight], [duration of illness] and [DAS28-4CRP at treatment start] as the quantitative data.

Note: This form should be prepared only at the time of literature analysis.

“Table 6.2.7.1 DAS28-4CRP Score of Week 24 and Mean Usage MTX dose Change from Week 24 to Week 52”

Analysis object: Patients included in the efficacy analysis set (DAS28-4CRP)

Purpose of analysis: Regarding the frequency of DAS28-4CRP Remission (< 2.6) at week 24, indicate from week 24 to week 52 by MTX dose reduction and compare them between the factors by χ^2 test.

Furthermore, a scatter graph with the DAS28-4CRP score at week 12 by patient as the Y axis and the change in MTX dose from week 24 to week 52 as the X axis should also be illustrated.

Note: The following tables should also be created with the same layout .

“Table 6.2.7.2 DAS28-4CRP Score of Week 24 and Mean Usage MTX dose Change from Week 24 to Week 104”

Note: The change in MTX dose from week 24 to week 104 should be compared in this form.

“Table 6.2.7.3 DAS28-4CRP Score of Week 12 and Mean Usage MTX dose Change from Week 12 to Week 52”

Note: The change in MTX dose from week 12 to week 52 and DAS28-4CRP Remission (< 2.6) at week 12 should be compared in this form.

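### Dropping MTX records of 0 mg, with no rule that time off MTX counts as zero, removes complete MTX withdrawal from the dose-by-visit and dose-change tables and leaves the mean-dose groups open to misclassification

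*SAP*

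**What the plan says.** In the derivation table of SAP 10.1, the row on the start date of MTX treatment first explains how to merge overlapping records and then states: "The records with the dose of 0 mg should be excluded from the analysis". The same sentence appears in the Humira rows beside the injection count, where it does no harm.

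SAP 9.1 adds: "Missing data should not be complemented in the analysis".

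Several forms in SAP 13.3 then need the MTX dose over time:

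- Table 6.2.5 compares DAS28-4CRP response between "two groups of the mean MTX dose at week 52: < 12.0 mg/week group or ≥ 12.0 mg/week group", and its note describes the grouping as "based on the increase and decrease of the mean MTX dose from the start of Humira treatment to week 52".
- Table 7.1 summarises, among others, "the mean MTX dose between treatment start and week 52".
- Table 6.2.2 forms three groups "based on the increase and decrease of the MTX dose from the start of Humira treatment to week 52".
- Table 6.2.7.1 takes week-24 remission and asks the analyst to "indicate from week 24 to week 52 by MTX dose reduction and compare them between the factors". Tables 6.2.7.2 to 6.2.7.4 repeat this for other windows.
- Table 7.1.1 charts the MTX dose at treatment start and at weeks 12, 24, 52, 76 and 104.

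The SAP gives no formula or denominator for the mean MTX dose, no rule that time off MTX is 0 mg, and no category for patients who stopped MTX. For Humira, by contrast, the Table 3.1 note in SAP 13.2 says that washout is included in the period to treatment completion.

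**The concern.** Protocol 7.5 ends observation before week 52 only when adalimumab stops, and after week 52 only when another biologic starts. Stopping MTX ends nothing, so such patients stay under observation, and Protocol 7.6.2 collects their MTX treatment at every follow-up visit. A rule about 0 mg records presupposes that such records can occur. It therefore discards documented withdrawal rather than tidying up missing data.

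The study is about adalimumab with MTX at 12 mg/week or more. The affected forms are the ones that show how much MTX patients actually took, whether disease activity differed by sustained dose, and whether early remission was followed by MTX reduction. A patient who stopped MTX altogether is highly informative for those questions. Under the plan as written, that patient can be absent from the change tables or counted among those who kept the high dose. The direction of any distortion in the DAS28 comparisons depends on why patients stopped (intolerance or remission, for example), which the documents do not tell us.

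**Working it through.** The plan states no mean MTX dose, so there is no figure to reproduce. The check follows a patient through the rules and then compares two denominators.

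**Inputs from the documents.** Lowest entry dose 12 mg/week (Protocol 7.2.1); 14 mg/week as a category boundary (SAP 10.1); maximum 16 mg/week (Protocol 5.0); week 52 at 364 days (SAP 12); cut-off 12.0 mg/week (Table 6.2.5).

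**Assumptions.** A constant dose D until MTX stops, and the stop weeks used below.

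**Step 1: dose at a visit.** A patient stops MTX, continues adalimumab, and the stop is entered as 0 mg. SAP 10.1 removes the record and SAP 9.1 forbids filling the gap. There is then no week-52 MTX dose for Table 6.2.2 and no entry for that visit in Table 7.1.1. Counted as 0, the change from 12 mg/week would be −12, well inside the lowest category of Table 6.2.2 (below −2).

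**Step 2: mean dose to week 52.**

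- (a) Remaining records only: Σ(dose × days) / Σ(days with dose > 0) = D, whatever the stop week.
- (b) Full window: Σ(dose × days) / 364, which equals D × (stop week)/52.

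| D (mg/week) | (a) any stop week | (b) stop at week 12 | (b) stop at week 24 | (b) stop at week 39 |
|---|---|---|---|---|
| 12 | 12.0 | 2.77 | 5.54 | 9.0 |
| 14 | 14.0 | 3.23 | 6.46 | 10.5 |
| 16 | 16.0 | 3.69 | 7.38 | 12.0 |

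Under (a), every row is in the group at or above 12.0. Under (b), only the last cell is. At a constant dose the two methods classify differently when the stop comes before week 52 × 12/D: week 52 for 12 mg, 44.6 for 14 mg, 39 for 16 mg.

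**Step 3: change from week 24 to week 52 (Table 6.2.7.1).** If the change uses visit doses, a patient off MTX at week 52 has no value, as in Step 1. If it uses window means, which the table title suggests:

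- Stop at week 24: no record remains in the window, so there is no value. Counted as zero, the change is −12, −14 or −16.
- Stop at week 36: the mean over remaining records is D, so the change is 0. Over the full 28 weeks the mean is D × 12/28 = 5.14, 6.00 or 6.86, a change of −6.86, −8.00 or −9.14.

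**The case against.** The strongest reply is that the SAP never says how the mean is formed. If total dose is divided by all calendar days to week 52, a dropped 0 mg record contributes nothing either way, and the week-12 stopper still averages 12 × 12/52 = 2.8. That stands. A reader might infer that the exclusion necessarily inflates mean MTX exposure; the documents do not support that, because the inflation needs a denominator of non-zero days that is not written anywhere. The calendar-day denominator is not written either, so two programmers could classify the same patient differently. Nor does it supply a week-52 dose for Table 6.2.2 or a visit dose for Table 7.1.1.

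Second, the sentence sits in a start-date row and may be meant only as record cleaning, since a 0 mg line is not a treatment start. That is plausible, but the wording reaches the analysis as a whole. It is also true that where a stop is shown only by a completion date, there is no 0 mg record to exclude. The exclusion is then idle, but the dose after stopping is just as undefined.

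Third, the titles of Tables 6.2.5 and 6.2.7.x speak of usage, and the dose while on MTX is a legitimate summary. It answers a different question from exposure over the window, and the SAP should say which it means.

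Fourth, the reach is limited: Tables 6.2.2, 6.2.5, 7.1 and 7.1.1 are marked for the literature analysis only. That stands. The entries for Tables 6.2.7.1 to 6.2.7.4 carry no such note.

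**Conclusion.** The point holds for the dose-by-visit and dose-change tables. Followed literally, the plan removes recorded complete withdrawal from Tables 7.1.1, 6.2.2 and 6.2.7.1 to 6.2.7.4, or, for a window mean over remaining records, can show it as no change. For Tables 6.2.5 and 7.1 it holds conditionally: the mean is 12.0 rather than 2.8 mg/week for a week-12 stop from 12 mg/week only if it is taken over non-zero records.

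Three further inferences are not supported:

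- That every patient who stops before the break-even weeks is misclassified. Those weeks need a constant dose. A patient on 12 mg for 4 weeks, 16 mg up to week 48 and then off MTX averages (12 × 4 + 16 × 44)/52 = 14.5 over the full window and belongs in the higher group by either method.
- That the last non-zero dose will be carried forward to week 52. SAP 9.1 points the other way.
- That a number of affected patients can be given. The documents contain no rate of MTX discontinuation, so it cannot be computed.

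The primary endpoint (DAS28 below 2.6 at week 52), the sample size and the baseline MTX strata are unaffected. This is a correction to supportive exposure tables, worth making because a stated rule discards collected data.

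**What to change.** Remove the 0 mg exclusion for the MTX dose and dose-change tables. It may stay for the Humira dose count and for deriving MTX start dates.

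Define the mean MTX dose as Σ(dose × days) divided by all days in the window from the start of Humira to week 52 or the end of observation. Count time off MTX as 0, whether it is shown by a 0 mg record or by a completion date. Apply the same definition to the other windows in Tables 7.1 and 6.2.7.1 to 6.2.7.4.

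At visits where the patient is recorded as off MTX, use 0 mg/week. Show it as its own segment in Table 7.1.1 and count it as a reduction in Tables 6.2.2 and 6.2.7.1 to 6.2.7.4. The mean dose while on MTX may be reported alongside, labelled as such.

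The cost is a short SAP edit and minor programming, with no new data. The downside is that the reported mean MTX doses become lower.
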